## 5.2. Dose Modification and Study Drug Discontinuation Rules

### 5.2.1. Dose Modification

Dose modification for an individual patient is not allowed.

### 5.2.2. Study Drug Discontinuation

Patients who permanently discontinue from study drug will be asked to return to the clinic for early termination assessments, per Section 6.2.8.

#### 5.2.2.1. Reasons for Permanent Discontinuation of Study Drug

Patients will be permanently discontinued from study drug dosing in the event of:

- Anaphylactic reaction or other severe systemic reaction to study drug
- Diagnosis of a malignancy during study, excluding carcinoma in situ of the cervix, or squamous or basal cell carcinoma of the skin
- Pregnancy at any time during the study
- Any infection that is opportunistic, such as active tuberculosis and other infections whose nature or course may suggest an immuno-compromised status
- Severe laboratory abnormalities that are judged to be related to dupilumab per criteria described in Section 7.3.2, such as:
  - Neutrophil count  $\leq 0.5 \times 10^3/\mu\text{L}$
  - Platelet count  $\leq 50 \times 10^3/\mu\text{L}$
  - Confirmed (by 2 separate tests at least 2 weeks apart) alanine aminotransferase (ALT) and/or aspartate aminotransferase (AST) values  $>3 \times$  upper limit of normal (ULN) and total bilirubin  $>2 \times$  ULN, excluding confirmed Gilbert's Syndrome
  - Confirmed AST and/or ALT  $>5 \times$  ULN (for more than 2 weeks)
- Inadequate efficacy:
  - Patients who show inadequate therapeutic response after at least 12 weeks of treatment with dupilumab will be discontinued from the study treatment based upon review of the case and joint decision by the investigator and medical monitor. For the purpose of this assessment, a review of efficacy will be triggered whenever patients fail to achieve and/or maintain EASI-25 (at least 25% improvement in the EASI score) at week 16, compared to the baseline score in the previous controlled and/or short-term study. Patients may also withdraw from the study at any time if they are not satisfied with the study treatment (see Section 4.3)
- Other reasons that may lead to the permanent discontinuation of study drug include:
  - Certain AEs deemed related to the study drug (eg, severe and prolonged ISRs)

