d Visits 10, 12, 14, and 16 have been removed per amendment 6. This yields a schedule in which visits are 8 weeks apart from week 16 through week 48. The week 48 visit is followed by a visit at 52 weeks; then visits occur every 8 weeks thereafter up to and including the end of treatment [EOT] visit.

e Visits 3, 4, 5, and 7 were removed per amendment 6.

f Patients who have completed their EOT visit as per amendment 7 may resume treatment with study drug at the next scheduled visit they would have attended if they had not had an EOT visit.

g Patients who have completed their end of study (EOS) visit as per amendment 7 will be re-evaluated for eligibility at a trial Re-Entry visit. Patients eligible to re-enter the trial may resume treatment at the next scheduled visit they would have attended if they had not completed the study. Patients are not eligible to re-enter the trial if more than 12 weeks have elapsed since their EOS visit.

h Visits 26, 28, 32, 34, 36, 38, 40, and 42 were removed per amendment 9.

i Approximately 50 patients who have not completed visit 44 (EOT) prior to implementation of amendment 10 will be asked to participate in a sub-study using the new dupilumab product. Eligible patients will enter the sub-study at either visit 41, 43, or 44 of the main study. This optional sub-study requires a separate consent.

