9. Any active infection requiring systemic treatment; patients with such infection must have their infection resolved at least 1 week before baseline to be eligible to enroll in the study.
10. Known or suspected immunodeficiency, including history of invasive opportunistic infections (eg, tuberculosis, histoplasmosis, listeriosis, coccidioidomycosis, pneumocystosis, aspergillosis) despite infection resolution, or otherwise recurrent infections of abnormal frequency as judged by the investigator.
11. Known history of human immunodeficiency virus (HIV) infection or HIV seropositivity (HIV testing is not required at screening for patients with a negative HIV result within the past 1 year prior to baseline).

12. Known history of positive hepatitis B surface antigen (HBsAg), hepatitis B core antibody (HBcAb), or hepatitis C antibody. If a patient has a documented negative result for any of these tests within 1 year of baseline, that particular test is not required at screening. Patients with isolated positive HBcAb or with positive hepatitis C antibody may undergo additional tests and consultations, and may enter the study only if active hepatitis B infection or carrier status has been definitively ruled out, subject to medical monitor's written approval.
13. History of clinical endoparasite infection within 12 months of the baseline visit, other than treated vaginal trichomoniasis.
14. Presence of skin comorbidities that may interfere with study assessments.
15. History of malignancy within 5 years before the baseline visit, except completely treated in situ carcinoma of the cervix, completely treated and resolved non-metastatic squamous or basal cell carcinoma of the skin.

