### 5.2.2.2. Reasons for Temporary Discontinuation of Study Drug

Study drug must be discontinued in case of:

- Severe laboratory abnormalities (as noted in Section 5.2.2.1) where a causal relationship to dupilumab can be reasonably excluded (ie, an alternative cause is evident). In these cases, study treatment will be discontinued (at least 1 dose while the clinical circumstances are being assessed), but it may be resumed when the laboratory parameters normalize sufficiently. A decision to resume study treatment will be made jointly by the investigator and the medical monitor.

Study drug dosing may be temporarily discontinued in the event of:

- Clinically important laboratory abnormalities, such as:
  - Neutrophil count  $\leq 1.0 \times 10^3/\mu\text{L}$  but  $> 0.5 \times 10^3/\mu\text{L}$
  - Platelet count  $\leq 100 \times 10^3/\mu\text{L}$  but  $> 50 \times 10^3/\mu\text{L}$
  - Creatine phosphokinase (CPK)  $> 10 \times \text{ULN}$ , unless the increase can be clearly attributed to physical exertion and considered clinically inconsequential.
- Other intercurrent illnesses or major surgery
- Any severe infection; any bacterial or viral infection requiring systemic treatment and remaining unresolved after 2 weeks of appropriate treatment; any clinical helminth endoparasitosis; any opportunistic infection
- Treatment with a live (attenuated) vaccine. Study drug dosing will be suspended for at least 12 weeks. NOTE: If the need for live vaccination is known in advance, to the extent possible, stop study drug for 12 weeks prior to vaccination
- Treatment with systemic nonsteroidal immunosuppressive/immunomodulating medications (eg, cyclosporine, methotrexate, azathioprine, mycophenolate-mofetil, Janus kinase inhibitors, biologic agents, etc)

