After the condition leading to temporary discontinuation of study drug resolves and/or the laboratory abnormality leading to suspension of dosing normalizes sufficiently, study drug dosing may resume at the discretion of the principal investigator in consultation with the medical monitor. Similarly, study treatment may resume after the medication leading to suspension of dosing has been discontinued. A decision to temporarily discontinue study drug and/or to resume study drug dosing should be discussed with the medical monitor. Resumption of study drug will require the medical monitor's written approval. The investigator may discontinue study drug dosing at any time, even without consultation with the medical monitor if the urgency of the situation requires immediate action and if this is determined to be in the patient's best interest. However, the medical monitor should be contacted as soon as possible in any case of study drug discontinuation. Resumption of study treatment after temporary discontinuation should always be discussed with the medical monitor and will require the medical monitor's written approval.

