**6.2.4. Visit 31/Day 1093/Week 156 through Visit 43/Day 1765/Week 252 (+/-3 Days)**

The study treatment duration will be up to 5 years. Visits 31 through 43 will occur approximately every 8 weeks until the end of treatment.

The following information will be collected:

- Concomitant medications/procedures: visit 31, 33, 35, 37, 39, 41, and 43.
- AEs
- Informed consent for the optional sub-study using the new dupilumab drug product: visit 41 or 43. See Section 6.2.6 for further information about procedures and assessments to be performed during the sub-study.

The following procedures and assessments will be conducted:

- IGA/EASI: visit 31, 37
- Weight: visit 31, 33, 35, 37, 39, 41, and 43
- Vital signs (heart rate, blood pressure, body temperature, and respiration rate): visit 31, 33, 35, 37, 39, 41, and 43
- Ophthalmology exam (select sites and patients): visit 31, 33, 35, 37, 39, 41, and 43)
- Patient assessment of pruritus intensity via IVRS/IWRS (weekly)
- Laboratory samples:
  - Hematology w/differential: visit 37
  - Serum chemistry: visit 37
  - Urine pregnancy test – for women of childbearing potential. Starting at visit 31 monthly until visit 43, urine pregnancy test must be negative before dosing.
  - ADA sample: visit 33 and 39
- Confirm that the patient completed/reported the dosing diary for each dose of study drug that was administered outside of the clinic
- Study drug dispensation/ accountability
- Administer study drug (weekly throughout the study)

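### An opportunistic infection requires permanent discontinuation under Protocol 5.2.2.1 but only an optional, reversible hold under 5.2.2.2, and no text says which rule prevails

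*Protocol*

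**What the plan says.** Protocol 5.2.2.1 lists events after which patients *will* be taken off study drug for good. One of them is "Any infection that is opportunistic, such as active tuberculosis and other infections whose nature or course may suggest an immuno-compromised status".

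Protocol 5.2.2.2 has two parts. The first is mandatory and covers severe laboratory abnormalities "where a causal relationship to dupilumab can be reasonably excluded". The second lists events for which dosing *may* be suspended, and its infection entry ends with "any clinical helminth endoparasitosis; any opportunistic infection". The closing paragraph says that after the condition resolves "study drug dosing may resume at the discretion of the principal investigator in consultation with the medical monitor". It also states, twice, that resumption needs the medical monitor's written approval.

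Two other places bear on this:

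- Exclusion criterion 10 in Protocol 4.2.2 keeps out patients with "Known or suspected immunodeficiency, including history of invasive opportunistic infections (eg, tuberculosis, histoplasmosis, listeriosis, coccidioidomycosis, pneumocystosis, aspergillosis) despite infection resolution".
- Protocol 6.2.4, covering Visits 31 to 43, says "Visits 31 through 43 will occur approximately every 8 weeks until the end of treatment" and "Administer study drug (weekly throughout the study". Figure 1 footnote h says "Visits 26, 28, 32, 34, 36, 38, 40, and 42 were removed per amendment 9". Section 5.1 moves patients still in the study at Amendment 9 to dosing every 2 weeks.

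**The concern.** The same unqualified event sits in a mandatory permanent list and in an optional temporary list, with a route back to dosing under the second. An investigator or medical monitor who relies on 5.2.2.2 can restart drug in a patient whom 5.2.2.1 says must never be dosed again. Read by itself, 5.2.2.2 also makes the initial hold a matter of choice.

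Patient safety is the main issue. There is also an effect on what gets reported. The class of TEAEs leading to permanent discontinuation (Protocol 9.5.2.1, SAP 5.8.1) depends on which section was followed. SAP 5.6 counts exposure from first to last injection without subtracting unplanned interruptions, so a patient who is held and restarted keeps accruing exposure while one who is stopped does not. Two patients with the same infection could be classified differently.

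The leftover in Section 6.2.4 is a separate and smaller matter: it describes a dosing frequency and a visit interval that Amendment 9 replaced.

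**Working it through.** No power, sample-size or event-rate arithmetic applies to the main point. The check is a comparison of the two rules.

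| Feature | Section 5.2.2.1 | Section 5.2.2.2, second list |
|---|---|---|
| Force | Mandatory | Optional |
| Event | Any opportunistic infection | Any opportunistic infection |
| Limit by severity, causality or confirmation | None | None |
| Return to dosing | None provided | Allowed after resolution, with written approval |

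**Do the two sets overlap?** Yes. One could try to confine 5.2.2.1 to infections that suggest impaired immunity, but its entry opens with any opportunistic infection and adds the others. Every opportunistic infection therefore falls under both sections.

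**Is there a tie-break?** None was found in the protocol or the SAP. The SAP has no dosing rule for this event.

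**Does the protocol separate other events that appear in both lists?** Yes, each time:

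- Severe laboratory abnormalities are split by causality. Those judged related to dupilumab are permanent under 5.2.2.1. Those where causality can be excluded are a mandatory hold under 5.2.2.2, with a cross-reference.
- Neutrophil counts are split by threshold: at or below 0.5 × 10³/µL in 5.2.2.1, and above 0.5 up to 1.0 × 10³/µL in the optional list.
- Platelet counts are split in the same way: at or below 50 × 10³/µL, and above 50 up to 100 × 10³/µL.

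Opportunistic infection is the one named event in both lists with no dividing condition.

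**Has the sponsor corrected this kind of overlap before?** Yes. The Amendment 3 entry in the amendment history records removing ALT, AST and bilirubin criteria from 5.2.2.2 because 5.2.2.1 already made them permanent. This is cited as precedent only.

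**Secondary point, visits in Section 6.2.4.** Inputs: Visit 31 is at Week 156 and Visit 43 at Week 252 (Protocol Tables 5 and 6).

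- Span: 252 − 156 = 96 weeks.
- At the stated 8-week interval: 96/8 + 1 = 13 visits.
- On the current schedule (odd-numbered visits, 16 weeks apart): 96/16 + 1 = 7 visits, at Weeks 156, 172, 188, 204, 220, 236 and 252.
- Removed in this range: 13 − 7 = 6 visits (32, 34, 36, 38, 40 and 42), which agrees with Figure 1 footnote h.

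Figure 1 footnote d carries the same 8-week wording through to the end of treatment.

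**The case against.** The strongest reply is that a mandatory rule and a permissive one can both be obeyed. A site that stops drug permanently breaches nothing in 5.2.2.2, because an option to suspend never obliges anyone to resume, and resumption is gated by the medical monitor rather than left to about 500 sites. That is a sensible reading, but it is not written down. The approval gate also does not settle the matter, because the monitor is the person who must choose between the two sections. A site that treats the hold as optional and keeps dosing never reaches the approval step.

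Second, exclusion criterion 10 concerns invasive infections only, so it does not show that every opportunistic infection should end treatment. The re-entry criteria in Section 4.2.3 do not name opportunistic infection; they ask that an active infection needing systemic treatment be resolved at least 1 week earlier, and leave the rest to judgement. This stands. Criterion 10 gives limited support to the stricter reading, and the main conclusion does not need it.

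Third, the protocol does not define an opportunistic infection beyond its example and general description. The SAP search list for the AESIs of Amendments 4 and 5 (Appendix 10.6) includes herpes viral infections, herpes zoster, eczema herpeticum and oropharyngeal candidiasis. On so broad a list, permanent discontinuation may be stricter than intended. That is a fair reason to consider a definition, but 5.2.2.1 already requires permanent discontinuation for these events, so deleting the duplicate entry adds no new obligation.

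Fourth, the entry may be an editorial import. Amendment 6 aligned the severe-infection hold text with the AESI criteria, and the older AESI list in SAP 4.6.1 resembles it closely. This is a plausible inference. It explains the conflict without removing it.

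On Section 6.2.4, the reply largely succeeds. The body of Figure 1 gives intervals of 8 to 16 weeks for Visits 31 to 43, the synopsis gives 4 to 16 weeks, and the visit-specific assessments in 6.2.4 name only odd-numbered visits.

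**Conclusion.** The concern holds. The protocol gives two incompatible instructions for the same event and no rule for choosing between them. It should be fixed, because it is a safety stopping rule and the correction is nearly free.

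Its size cannot be stated in patients, since neither document reports how many opportunistic infections occurred. No formula or sample-size statement changes; the analytic effect is limited to which patients are classed as permanently discontinued and how much exposure they accrue. The conclusion rests on reading both entries as covering any opportunistic infection, which is what each says.

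The 6.2.4 leftover is real (13 visits implied against 7 scheduled) but low risk, because dosing every 2 weeks is clear in the synopsis, Sections 3.1 and 5.1, and the schedule-table footnotes.

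**What to change.** Make one of two changes in Section 5.2.2.2:

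1. Delete the opportunistic-infection entry from the optional list, leaving 5.2.2.1 as the only rule; or
2. Move it to the mandatory part, worded along these lines: study drug must be held for a suspected opportunistic infection until it is confirmed or ruled out; if confirmed, Section 5.2.2.1 applies.

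If the sponsor means some opportunistic infections to permit resumption, that limit belongs in 5.2.2.1 itself, as a definition or an invasive versus non-invasive split.

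In Section 6.2.4, replace the weekly-dosing and 8-week wording with a cross-reference to Section 5.1 and Figure 1. Correct Figure 1 footnote d at the same time, so that the cross-reference does not bring the 8-week interval back.

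The cost is a protocol clarification letter or a wording change in the next amendment, with no analysis or sample-size cost.

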### 5.2.2.2. Reasons for Temporary Discontinuation of Study Drug

Study drug must be discontinued in case of:

- Severe laboratory abnormalities (as noted in Section 5.2.2.1) where a causal relationship to dupilumab can be reasonably excluded (ie, an alternative cause is evident). In these cases, study treatment will be discontinued (at least 1 dose while the clinical circumstances are being assessed), but it may be resumed when the laboratory parameters normalize sufficiently. A decision to resume study treatment will be made jointly by the investigator and the medical monitor.

Study drug dosing may be temporarily discontinued in the event of:

- Clinically important laboratory abnormalities, such as:
  - Neutrophil count  $\leq 1.0 \times 10^3/\mu\text{L}$  but  $> 0.5 \times 10^3/\mu\text{L}$
  - Platelet count  $\leq 100 \times 10^3/\mu\text{L}$  but  $> 50 \times 10^3/\mu\text{L}$
  - Creatine phosphokinase (CPK)  $> 10 \times \text{ULN}$ , unless the increase can be clearly attributed to physical exertion and considered clinically inconsequential.
- Other intercurrent illnesses or major surgery
- Any severe infection; any bacterial or viral infection requiring systemic treatment and remaining unresolved after 2 weeks of appropriate treatment; any clinical helminth endoparasitosis; any opportunistic infection
- Treatment with a live (attenuated) vaccine. Study drug dosing will be suspended for at least 12 weeks. NOTE: If the need for live vaccination is known in advance, to the extent possible, stop study drug for 12 weeks prior to vaccination
- Treatment with systemic nonsteroidal immunosuppressive/immunomodulating medications (eg, cyclosporine, methotrexate, azathioprine, mycophenolate-mofetil, Janus kinase inhibitors, biologic agents, etc)

After the condition leading to temporary discontinuation of study drug resolves and/or the laboratory abnormality leading to suspension of dosing normalizes sufficiently, study drug dosing may resume at the discretion of the principal investigator in consultation with the medical monitor. Similarly, study treatment may resume after the medication leading to suspension of dosing has been discontinued. A decision to temporarily discontinue study drug and/or to resume study drug dosing should be discussed with the medical monitor. Resumption of study drug will require the medical monitor's written approval. The investigator may discontinue study drug dosing at any time, even without consultation with the medical monitor if the urgency of the situation requires immediate action and if this is determined to be in the patient's best interest. However, the medical monitor should be contacted as soon as possible in any case of study drug discontinuation. Resumption of study treatment after temporary discontinuation should always be discussed with the medical monitor and will require the medical monitor's written approval.

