Approximately 50 patients who are participating in the current ongoing OLE study (R668-AD-1225) and have not completed the end of treatment visit (ie, visit 44) prior to the implementation of amendment 10 will be asked to participate in the sub-study. After providing informed consent, eligible patients who agree to participate will enter the sub-study at either visit 41, 43, or 44 of the main study and have study treatment switched from the current dupilumab drug product to the new dupilumab drug product at sub-study visit 1a. Dupilumab dosing will remain 300 mg SC q2w, and patients will be treated with the new dupilumab drug product 300 mg SC q2w for at least 12 weeks (some patients may be treated for 24 weeks). The end of study visit for patients participating in the sub-study under amendment 10 will be 84 days (12 weeks) after the last dose using the new dupilumab drug product. Patients who enter the sub-study from either visit 43 or visit 44 of the main study will have the duration of their study treatment increased by 4 or 12 weeks, respectively.

Patients and/or caregivers who are willing and able to administer dupilumab doses outside the clinic will be trained on injecting study drug unless they had already been trained during their participation in the previous study. These patients will self-inject study drug (or have the drug administered by a caregiver) during weeks in which no clinic visit is scheduled. Safety, laboratory, and clinical assessments will be performed at specified clinic visits.

Patients who receive treatment with a prohibited or restricted medication will be discontinued from study drug for the duration of the prohibited treatment (plus 5 half-lives as applicable). Study treatment may be resumed only if approved by the medical monitor.

Patients who test positive for anti-drug antibody (ADA) at their last study visit (early termination or end of study) may, based on the benchmark ADA titer in effect at the time, be asked to return to the clinic to have additional ADA samples collected for analysis within 6 to 12 months after their last dose of study drug, and thereafter at intervals of approximately 3 to 6 months until their titers fall below the benchmark titer.

|                           |  |
|---------------------------|--|
| Study Duration     | The study treatment duration will be up to 5 years.  |
| Population         |  |

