### 5.5.2. Prohibited and Restricted Medications

Concomitant treatment with the following medications is prohibited during the study. These medications should generally be avoided, but if they are medically necessary (eg, as a rescue treatment for intolerable AD symptoms or to manage serious intercurrent conditions), they may be administered while the study drug is discontinued.

- Treatment with nonsteroidal systemic immunosuppressive medications (including, but not limited to, cyclosporine, mycophenolate-mofetil, IFN- $\gamma$ , azathioprine, methotrexate, or other immunomodulating biologics\*)
- Treatment with an investigational drug\* (other than dupilumab)

- Live (attenuated) vaccines\*\*

|  |                                |
|--|--------------------------------|
| Chickenpox (Varicella)                             | Oral typhoid                   |
| FluMist-Influenza                                  | Rubella                        |
| Intranasal influenza                               | Smallpox (Vaccinia)            |
| Measles (Rubeola)                                  | Yellow fever                   |
| Measles-mumps-rubella (MMR) combination            | Bacillus-Calmette–Guérin (BCG) |
| Measles-mumps-rubella-varicella (MMRV) combination | Rotavirus                      |
| Mumps  | Varicella Zoster (shingles)    |
| Oral polio (Sabin)                                 |                                |

- \* Patients who receive an immunomodulating biologic or investigational drug will be discontinued from study drug for the duration of treatment with these medications, plus 5 half-lives (if known) or 16 weeks, whichever is longer.
- \*\* In the case of live vaccines, study treatment should optimally be stopped 12 weeks before vaccine administration and may not resume sooner than 12 weeks after vaccine administration.

In all cases, the resumption of study treatment must be approved by the medical monitor.

Patients who discontinue study treatment permanently will be asked to complete the assessments of the early termination and end of study visits.

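### Protocol Section 5.2.2.2 makes the hold for systemic nonsteroidal immunosuppressants and biologics optional and gives no washout before restart, in conflict with the mandatory hold and washout in the Synopsis and Sections 3.1 and 5.5.2 (minor)

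*Protocol*

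**What the plan says.** Protocol Section 5.2.2.2 contains two lists. The mandatory one holds a single item: severe laboratory abnormalities for which a causal link to dupilumab can reasonably be excluded. The second begins "Study drug dosing may be temporarily discontinued in the event of" and includes "Treatment with systemic nonsteroidal immunosuppressive/immunomodulating medications", with cyclosporine, methotrexate, azathioprine, mycophenolate, Janus kinase inhibitors and biologics as examples. Nothing attached to that item makes the hold compulsory. The live-vaccine item on the same list does carry such a sentence: "Study drug dosing will be suspended for at least 12 weeks".

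On restart, the same section says "Similarly, study treatment may resume after the medication leading to suspension of dosing has been discontinued". It adds "A decision to temporarily discontinue study drug and/or to resume study drug dosing should be discussed with the medical monitor", and it states twice that resumption needs the medical monitor's written approval. It gives no interval after the other drug is stopped and does not point to another section.

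Elsewhere the rule is firm. In the Synopsis, and in the same terms in Section 3.1, patients given a prohibited or restricted medication "will be discontinued from study drug for the duration of the prohibited treatment (plus 5 half-lives as applicable". Section 5.5.2 prohibits nonsteroidal systemic immunosuppressants. Where such drugs are medically necessary, "they may be administered while the study drug is discontinued". For immunomodulating biologics and investigational drugs, the hold lasts for the course of treatment "plus 5 half-lives (if known) or 16 weeks, whichever is longer".

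**The concern.** Section 5.2.2.2 is the section titled for temporary holds. Read on its own, it presents as discretionary a hold that three other places in the protocol require, and it allows restart without a reminder of the washout.

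The situation is one the protocol expects. Section 5.5.2 foresees these drugs as rescue when AD symptoms become intolerable, and Section 8.2.2 counts use of systemic immunosuppressive drugs as a rescue endpoint. In a long-term safety study, two sites facing the same event should not be able to find different instructions in the same protocol. At stake is consistent patient protection: whether a patient goes on receiving dupilumab while taking a drug that the protocol says must not be combined with it.

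The point is confined to the nonsteroidal class. Section 5.5.1 permits systemic corticosteroids alongside study drug.

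**Working it through.** The plan states no figure on this point, so the check is a comparison of text, followed by one conversion of units.

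**Hold**

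| Place | Status of the hold for this class |
|---|---|
| Section 5.2.2.2 | Optional (permissive list, no overriding sentence) |
| Synopsis; Section 3.1 | Mandatory for the duration of the other treatment |
| Section 5.5.2 | Class prohibited; usable only while study drug is stopped |

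**Washout before restart**

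| Place | Interval |
|---|---|
| Section 5.2.2.2 | None stated; other drug stopped, plus written approval |
| Synopsis; Section 3.1 | 5 half-lives as applicable |
| Section 5.5.2 | Biologics and investigational drugs only: the longer of 5 half-lives or 16 weeks |

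1. The permissive wording cannot be put down to list style alone. The live-vaccine item shows that the authors added a compulsory sentence under that heading where they wanted one. The immunosuppressant item has none.
2. The two washout rules outside 5.2.2.2 do not conflict with each other. Section 3.1 gives a general rule and Section 5.5.2 a stricter one for two classes. But the interval in 5.5.2 is tied by footnote to those two classes, so a pointer to 5.5.2 alone would leave conventional agents such as cyclosporine or methotrexate without an interval. For them the interval comes from Section 3.1.
3. Size of the unmentioned rule. Section 3.1 gives two-weekly dosing after amendment 9. For a biologic or investigational drug the minimum washout is 16 weeks, and 16 / 2 = 8 dosing intervals. The vaccine interval that 5.2.2.2 does state is 12 weeks, and 12 / 2 = 6 intervals. These are the lengths of the rules, not estimates of how early anyone restarted.
4. Where the medical monitor comes in. Section 5.2.2.2 sends two decisions to the monitor: to hold and to resume. A site that reads the hold as optional and keeps dosing makes neither, so on the literal text the safeguard is not triggered. A site that does hold must obtain written approval before restarting. The gap is therefore mainly in the missed hold.

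**The case against.** The strongest reply is that no rule is really in doubt. Section 5.5.2 governs, it forbids the combination, and an investigator considering a prohibited rescue drug would reasonably open that section. The permissive heading also covers any opportunistic infection, which Section 5.2.2.1 makes a reason for permanent discontinuation, so the heading plainly does not override stricter rules elsewhere. The restart sentence speaks of a medication that led to suspension, which presupposes a hold, and it sets no zero-day interval. Both 5.2.2.2 and 5.5.2 require the monitor's approval before restart.

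Most of this stands, and it fixes the severity. It does not remove the conflict over the hold. One section says optional and the others say required, and the optional version carries no cross-reference. Section 5.2.2.2 also names Janus kinase inhibitors, which the open-ended examples in 5.5.2 do not, so a site searching the on-treatment rules by that name finds it only on the permissive list.

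A reader might go further and infer that the protocol authorises co-administration, or allows restart on the day the other drug stops. It does neither: no section permits the combination, and restart without written approval is not allowed. A reader might also infer bias in the safety or exposure results. The documents do not support that. They give no count of affected patients and no estimate of harm from overlap. SAP Section 5.6 computes exposure duration regardless of unplanned interruptions, and SAP Section 5.7 uses all observed efficacy values whether or not rescue was used.

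**Conclusion.** Wrong as written, minor. Section 5.2.2.2 conflicts with the Synopsis and Sections 3.1 and 5.5.2 on whether study drug must be stopped, and it omits the washout those places require. For a biologic or investigational drug, that omitted washout is at least 16 weeks, or 8 two-weekly intervals.

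The practical risk is limited to sites acting on 5.2.2.2 alone. It falls mainly on the hold, since restart already needs written approval. The conclusion rests only on the current protocol text and needs no assumption about half-lives, course lengths or frequency of use. It says nothing about the size or direction of any effect on an endpoint.

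**What to change.** Two edits to Section 5.2.2.2:

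1. Move the item on systemic nonsteroidal immunosuppressive and immunomodulating drugs, biologics included, from the permissive list to the mandatory one.
2. Reword the restart sentence so that dosing may resume only once the other medication has been stopped and the washout in Sections 3.1 and 5.5.2 has elapsed. That washout is 5 half-lives as applicable or, for biologics and investigational drugs, the longer of 5 half-lives or 16 weeks. Cite both sections, and keep the qualifier that the half-life rule applies as applicable, so that existing discretion for conventional agents is not narrowed.

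The written-approval requirement stays as it is. The Synopsis, Sections 3.1 and 5.5.2, and the SAP need no change.

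The cost is one list item moved and one clause added, with no new visits or procedures. Section 14 requires an IRB/EC-approved amendment for a change in operation. Enrollment has been closed since amendment 8, so the change reaches only patients still on treatment. It is best bundled with another amendment rather than issued alone.
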